11.2 STUDY DESIGN

This is a single-arm study with 2 strata: Stratum 1 for patients with osteosarcoma, and Stratum 2 for patients with other high risk solid tumors. Stratum 2 is exploratory in nature, and the goal of including these patients is to facilitate accomplishing secondary objectives related to toxicity and the feasibility of administering this treatment regimen to solid tumor patients. If possible, we will, however, use patients on Stratum 2 to estimate response rates of tumors other than osteosarcoma. For Stratum 1, 6-month PFS as the primary endpoint. The study will pre-specify target lesions for each patient in Stratum 1 that will be used to assess PFS, with the intention that every lesion radiographically evident at the time of enrollment will be a target lesion. Events will be the first disease progression at any of the target lesions or death from any cause. All patients treated on Stratum 1 will be included in the determination of PFS, regardless of treatment modification or discontinuation. The design will include interim analyses for futility if it seems unlikely that the treatment has sufficient activity. The historical PFS in 11 patients treated with ¹⁵³Sm-EDTMP similar to how we are proposing, but without the external beam component, was 15.8%. For this study of ¹⁵³Sm-EDTMP plus external beam radiation therapy, a 6-month PFS of 35% would be the lowest that would be considered acceptable, and PFS that is convincingly worse than this would be considered grounds for discontinuing further study. The non-parametric Kaplan-Meier estimate will be used to monitor the PFS function. After 8 patients have been enrolled, the design will include an interim analysis for futility that could halt the trial if it seems likely that this regimen does not have sufficient clinical activity. The study is designed to stop if we are 80% certain that the 6-month PFS is below 15%.

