The primary goal of this study will be to examine tumor response after radiation treatment via a combination of ^{153}Sm -EDTMP and external beam radiotherapy. A well-described characteristic of calcified osteogenic sarcoma lesions, as well as many bony metastases, is that despite necrosis or lack of viable tumor being detectable on histologic analysis, the tumor frequently does not shrink by radiographic imaging. Therefore the major clinical endpoint in evaluating clinical response will be lack of progression (stable disease or better by RECIST criteria). The favorable, manageable toxicity profile of ^{153}Sm -EDTMP would meet the needs of our study population of poor-risk, heavily pre-treated patients who might not otherwise be candidates for additional toxic therapy. This novel strategy of combined infusional and external-beam radiotherapy might prove to be an effective means for local control and offer significant clinical benefit.

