6.2 OVERALL TREATMENT PLAN

This is a treatment protocol to establish the safety and efficacy of radiation therapy consisting of high-dose ^{153}Sm -EDTMP and external beam radiotherapy for the treatment of high-risk osteogenic sarcoma and solid tumors with bony metastases. The primary endpoint will be clinical response of tumor lesions, defined as either stable disease or decrease in the size of the tumor by radiographic imaging (which may include CT or MRI) using RECIST 1.1 criteria. Progression will be defined as appearance of new lesions or expansion of current lesions by 20% as per RECIST 1.1 criteria. In some patients, additional information on clinical response may be obtained from histology (percent tumor necrosis) in cases where patients proceed to resection or biopsy following radiation therapy. Other treatment endpoints include progression-free and overall survival. We will obtain post-treatment [^{18}F]-MISO and [^{18}F] FDG PET scans to be analyzed but these images will not be used to define clinical response.

The first administered activity of ^{153}Sm -EDTMP will be a low “tracer” infusion administered at 1 mCi/kg on Day 1. Using the 3-dimensional dosimetry package 3D-RD, we will perform three-dimensional dosimetry using SPECT images after administration of the “tracer” activity to determine the distribution of dose delivered to the tumor and the surrounding normal tissues. As quickly as feasible (goal is within seven days), using the dosimetric results from the tracer administration, a combined treatment plan will be designed aimed at delivering the target dose to the entire tumor. This plan will be designed using methodology uniquely available at Hopkins (3D-RD software); we will import the 3-dimensional absorbed dose map resulting from ^{153}Sm -EDTMP therapy, adjusted to correspond to the fractionation schedule used in external beam radiotherapy, into the external beam planning system (Pinnacle), by fusing (registering) the SPECT/CT and absorbed dose map with the external beam planning CT, allowing a treatment plan to be generated from the combination of (1) scaling of the tracer absorbed dose map to the requisite ^{153}Sm therapeutic activity and (2) external beam fields designed to optimally complement the radiopharmaceutical absorbed dose map to deliver a target of 75 Gy to each and every tumor voxel while respecting normal organ constraints (25).

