11.0 STATISTICAL CONSIDERATIONS

11.1 OVERVIEW

This protocol will assess the proportion of clinical tumor responses, defined as progression-free survival at 6 months, and the toxicities associated with high-dose ^{153}Sm -EDTMP (MTD at 30 mCi/kg) after an initial lower dose of the agent along with external beam radiation therapy in patients with high-risk osteogenic sarcoma.

Primary objective: The primary objective of this study is to determine if the addition of external beam radiation therapy to infusional ^{153}Sm -EDTMP can delay the progression of target lesions. The primary endpoint is 6-month progression free survival (PFS). It is a combined effect of the entire treatment. To be evaluable, patients must meet all eligibility criteria, including signing a consent form, and have completed treatment according to protocol without major deviations. Patients who are enrolled but unevaluable will be replaced on the study. Only patients enrolled on Stratum 1 (i.e., with a diagnosis of osteosarcoma) will be evaluated for the Primary Objective.

Secondary objectives:

1. Describe the short and long-term toxicity profile of combined treatment with ^{153}Sm -EDTMP and external beam radiation therapy.
2. Estimate the local control rate. (Stratum 1 only)
3. Determine the overall survival (OS). (Stratum 1 only)
4. Describe the distribution of absorbed doses delivered to each targeted lesion and the distribution of equivalent uniform doses delivered to each patient.
5. Model the relationship between absorbed doses and time to progression.
6. Determine the correlation of hypoxic volume and maximum tumor/blood ratio obtained by [^{18}F]-MISO PET scanning with patient outcomes.

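### The Stratum 1 primary endpoint has conflicting definitions (response at one month, target-lesion PFS, any-progression PFS), and the plan does not say which events the 15.8% reference counted

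*Combined protocol and SAP*

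**What the plan says.** The combined protocol and SAP describes the Stratum 1 primary endpoint in several places.

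- **Section 3.1.1** gives the objective as clinical response, without a time point.
- **Section 6.2**: "The primary endpoint will be clinical response of tumor lesions, defined as either stable disease or decrease in the size of the tumor", by RECIST 1.1. It then adds: "Other treatment endpoints include progression-free and overall survival". Later in the same section, imaging for clinical response is set at one month after external beam ends. Progression in 6.2 includes new lesions.
- **Section 9.1.3** repeats the stable-disease-or-better definition, with no 6-month time point. **Section 9.1.1.5** also counts new lesions as progression.
- **Section 11.1**: "This protocol will assess the proportion of clinical tumor responses, defined as progression-free survival at 6 months". It names 6-month PFS as primary and asks whether adding external beam "can delay the progression of target lesions".
- **Section 11.2**: "Events will be the first disease progression at any of the target lesions or death from any cause". Target lesions are specified in advance, "with the intention that every lesion radiographically evident at the time of enrollment will be a target lesion".
- **Section 11.3.5** measures PFS from registration to the first documented progression or death, with no restriction to target lesions.

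The reference is a PFS of 15.8% in 11 patients given the radiopharmaceutical without external beam (Section 11.2). Section 11.3.1 gives its hazard and median. No section says which events it counted.

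**The concern.** Two kinds of patient change status with the section used. A patient whose treated lesions are stable but who develops a new metastasis at month 4 is event-free under 11.2, and a failure under 11.3.5 read with 6.2 and 9.1.1.5. A patient who is stable at the one-month scan and progresses before 6 months succeeds under 6.2 and fails under 11.1 to 11.3.

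The first kind of patient is plausible here. Section 4.1 says that conformal external beam cannot treat micrometastases, and Section 4.3 describes a poor-risk, heavily pre-treated population.

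There is no control arm to absorb a difference in definition. A single-arm test against a fixed external figure is valid only if trial and reference count the same events. If the reference counted new lesions and the trial does not, the test favours activity and the futility rule stops too seldom. If the mismatch runs the other way, power is lost.

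A lesser point: Section 9.1.1 mixes response rules based on products of diameters with RECIST 1.1. Its minor-response limit (no lesion growing by more than 25%) overlaps its progression limit (more than 20%).

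**Working it through.** **Inputs from Section 11.3.1:** null 6-month PFS 15.8%, benchmark 35%, N = 20, one-sided alpha 0.05, exponential survival, 5 years' accrual plus 1 year's follow-up, stated power 82% at a hazard ratio of 1.76.

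**Assumed input:** f, the share of the null hazard that is new lesions only. The documents do not give it. I show f = 10% and 25%, plus the value at which an inactive regimen reaches 35%. Hazards are taken as constant.

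**Step 1. Reproduce the plan.**
- Null hazard λ0 = −ln(0.158)/6 = 0.3075 per month (median 2.25 months).
- Benchmark hazard λ1 = −ln(0.35)/6 = 0.1750. Ratio 0.3075/0.1750 = 1.76.
- Expected events with this accrual and follow-up are 19.8 at λ1 and 20.0 at λ0, so take 20.
- With total follow-up time T, the exact exponential test rejects when 2·λ0·T exceeds the 95th percentile of chi-square on 40 df, which is 55.76.
- At true hazard h, P(reject) = P(χ²₄₀ > 55.76·h/λ0).
- At h = λ1 this is 82.2%, matching the plan's 82%. The power arithmetic is sound.

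**Step 2. Reference counted new lesions, trial uses 11.2, regimen inactive.** The trial sees h = λ0(1 − f), and 6-month PFS is exp(−6h). The value of f giving 35% is 1 − 0.1750/0.3075 = 43%. Futility stopping is linearly interpolated from the plan's table of interim operating characteristics.

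| f | 6-month PFS seen | P(reject 15.8%) | P(stop for futility) |
|---|---|---|---|
| 0 | 15.8% | 5% | about 36% |
| 10% | 19.0% | 13% | about 26% |
| 25% | 25.1% | 39% | about 12% |
| 43% | 35.0% | 82% | about 4% |

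**Step 3. Reference was target-lesion-only, trial counts any progression, target-lesion PFS truly 35%.** The trial sees h = λ1/(1 − f).
- f = 10%: h = 0.1944, PFS 31.1%, power 68%.
- f = 25%: h = 0.2333, PFS 24.7%, power 37%.

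**Step 4. Both matched on any progression, external beam slows target lesions only.** Here h = λ0·f + λ0(1 − f)/1.76.
- f = 10%: h = 0.1880, power 73%.
- f = 25%: h = 0.2079, power 57%.

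**Step 5. Both target-lesion-only.** Type I error and power are as planned.

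A normal approximation on the log hazard gives similar figures at f = 10%: 12% in place of 13% in Step 2, and 65% in place of 68% in Step 3.

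**The case against.** The best defence is that Section 11 governs. It defines clinical response as 6-month PFS and uses that endpoint for the objective, sample size, futility rule and analysis. The target-lesion event in 11.2 fits the objective in 11.1 and is a legitimate choice. Section 11.3.5 can be read as a general survival paragraph, which conflicts only when combined with 6.2 and 9.1.1.5. The one-month endpoint also has to be assembled: the endpoint sentence in 6.2 has no time point, and the one-month scan appears later in that section.

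Part of this stands. Section 3.1.1 can be reconciled through 11.1, and target-lesion PFS is a defensible endpoint. But no order of precedence is stated, and 6.2 expressly places PFS among the other endpoints. Section 11.3.5 uses the same term for the same stratum, while PFS is not among the secondary objectives in 11.1. Letting 11.2 govern still leaves the content of the 15.8% unknown.

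The fair objections to the size are these:
- f is unknown, and no mismatch has been shown.
- The 43% row was solved to reach 35%, so its 82% is the design power restated and not an independent estimate of risk.
- The test rejects at an estimated 6-month PFS of about 27% (hazard 20·2·0.3075/55.76 = 0.2206), whereas 11.2 calls 35% the lowest acceptable value. The binomial chance of seeing at least 7 of 20 (35%) with an inactive regimen is 3% with no mismatch, and 7%, 22% and 58% at f = 10%, 25% and 43%. These are smaller than the rejection rates, but they rise in the same way.

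The minor-response category in 9.1.1 feeds no stated decision rule, so that point is tidying.

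**Conclusion.** The concern holds. The primary event rule contradicts itself, so two analysts following the document could classify the same patient differently. The comparability on which the single-arm test depends is not established.

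The plan's power figure is correct on its own terms. The finding is an unverified comparison, not a demonstrated bias. For an assumed new-lesion share of 10% to 25% with constant hazards, the one-sided error rises from 5% to between 13% and 39% if only the reference counted new lesions. Power falls from 82% to between 68% and 37% if only the trial counts them. It must be fixed before the primary analysis. Confidence is high on the contradiction and on the missing reference definition; the size depends on f.

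**What to change.** Use one primary definition in Sections 3.1.1, 4.3, 6.2, 9.1.3, 11.1, 11.2 and 11.3.5: 6-month PFS from registration, stating explicitly whether a new lesion is an event. State what the 15.8% from the earlier 11-patient study counted, and match it.

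- **If it was target-lesion-only:** keep the 11.2 event, call it target-lesion PFS, and define any-progression PFS separately in 11.3.5.
- **If it counted new lesions:** either add new lesions to the 11.2 event and align the 11.1 objective, or keep 11.2 and re-derive the reference on the target-lesion definition. In the latter case, also review the 35% benchmark and the 15% futility threshold.

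Report the other PFS version and one-month clinical response as secondary. Reconcile the size criteria in 9.1.1 or label them exploratory.

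The cost is wording, and possibly a re-analysis of the earlier study's data. No patients or scans are added. If any-progression PFS is chosen, the estimate may be lower. If external beam slows only the treated lesions, power would be about 73% or 57% (f = 10% or 25%) even with a matched reference, and the plan should say so.

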11.3 STATISTICAL ANALYSIS PLAN

11.3.1 Estimate the PFS for subjects treated on Stratum 1.

Sample size: The primary measure of efficacy will be PFS at 6-months for Stratum 1 patients. In specific, the 6-month PFS for this treatment will be compared to a reference of 15.8% (hazard rate = 0.308/person-month i.e. median of 2.25 months). In patients with metastatic osteosarcoma a 6-month PFS of 35% would be considered promising, and is the benchmark for this study. Assuming exponential survival, 4 patients per year will be accrued for 5 years (20 total), one year of additional follow-up, and a one-sided 0.05 alpha level test, the sample size of 20 will have 82% power to detect a hazard ratio of 1.76.

Early stopping guideline for safety: The study will be monitored after every patient for non-hematologic grade 4 toxicities following initiation of external beam radiation therapy. This stopping rule for toxicity will hold enrollment if the posterior probability of risk being larger than 0.2 is 75% or higher. The prior for this toxicity monitoring rule is beta (1, 5). This distribution means that our prior guess at this type of grade 4 toxicity is 16.7%, and there is 95% probability that it is between 0.51% and 52.2%. The operating characteristics of the stopping rule are shown below and are based on 5000 simulations:

Toxicity stopping rule:

Study termination if:	2 AEs	3 AEs	4 AEs	5 AEs	6 AEs
And number of patients between:	2 - 3	4 - 7	8 - 12	13 - 16	17 - 20

Operating characteristics of stopping rule based on 5000 simulations:

True Toxicity Risk	Prob. Declare Treatment Too Toxic	Avg. Sample Size
0.05	1.0%	19.8
0.10	6.4%	19.2
0.15	17.1%	17.9
0.20	33.7%	16.2
0.25	54.0%	13.8
0.30	69.1%	12.0
0.35	82.9%	9.7
0.40	92.6%	7.9

Early stopping guideline for futility and simulations: Simulation is used to demonstrate the operating characteristics of the study for a sample size of 20. The study will be monitored for futility with a primary endpoint of 6-month PFS. The non-parametric Kaplan-Meier estimate will be used to estimate the PFS function at 6-months. After 8 patients have been enrolled, the design will include an interim analysis for futility that could halt the trial if it seems likely that the treatment does not have sufficient clinical activity.

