The sample size of 20 and the study design operating characteristics assume a 5 year accrual period with an additional follow-up of one year. The null 6-month PFS is 15.8%. We have designed the study to stop early only if the posterior probability of 6-month PFS being less than 0.15 is 80% or higher. Simulations were carried out with exponential survival and staggered patient entry. We assume on average 1 patient will enter the study every three months. Interim analyses begin once 8 patients have been entered on the study and occur after groups of 4 patients thereafter up to a maximum of 20 patients. The interim analysis estimates of 6-month PFS are based on analyses with an underlying Dirichlet process prior. We approximate the posterior distribution, which is actually a mixture of Beta distributions, the mixture depending on the amount of censoring, with a single Beta distribution. The parameters of this posterior Beta distribution are based on the number of failures and the effective sample size at 6-months, combined with the parameters of the prior.

The following table summarizes the operating characteristics of the futility stopping rule under various scenarios for the underlying exponential PFS, based on 5000 simulations. For futility monitoring we characterize the uncertainty of the 6-month PFS estimate with the prior: beta (1, 4). This implies that our prior guess at the 6-month PFS in this study is 20% and there is 90% certainty that the 6-month PFS is between 1.3% and 52.7%.

Table 2. Interim monitoring rule operating characteristics

6-month PFS	Prob Stop for Futility	Avg N	Estimated 6-mo PFS	lo 90% Post Int'l	hi 90% Post Int'l
0.10	0.60	14.2	0.07	0.0	0.20
0.15	0.39	16.2	0.12	0.0	0.30

0.20	0.23	17.7	0.18	0.0	0.35
0.25	0.12	18.7	0.23	0.0	0.40
0.30	0.07	19.2	0.29	0.0	0.45
0.35	0.04	19.6	0.34	0.15	0.50
0.40	0.02	19.8	0.40	0.20	0.60

Analysis for primary objective: Overall hazard rate estimates and 95% confidence intervals as well as Kaplan-Meier (KM) estimates will be used to summarize PFS over time. The 6-month PFS with 95% confidence interval will be reported.

11.3.2 Describe the toxicity profile of this regimen in the short and long-term.

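### Does the plan need a written decision rule at 35%, the 6-month PFS it calls the lowest acceptable?

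*Combined protocol and SAP*

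**What the plan says.** Section 11.2 (Study Design) states that "a 6-month PFS of 35% would be the lowest that would be considered acceptable, and PFS that is convincingly worse than this" would count against further study. It does not define the qualifier. The same section gives the interim rule: "The study is designed to stop if we are 80% certain that the 6-month PFS is below 15" percent.

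Section 11.3.1, under Sample size, says that "the 6-month PFS for this treatment will be compared to a reference of 15.8" percent, equivalent to a hazard of 0.308 per person-month. It describes the upper figure differently from Section 11.2: "In patients with metastatic osteosarcoma a 6-month PFS of 35% would be considered promising, and is the benchmark for this study". The design statement is that, with "a one-sided 0.05 alpha level test, the sample size of 20 will have 82% power to detect a hazard ratio of 1.76". The futility text later in 11.3.1 repeats that the null is 15.8%.

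The closing paragraph of 11.3.1, Analysis for primary objective, is about estimation: "Overall hazard rate estimates and 95% confidence intervals as well as Kaplan-Meier (KM) estimates will be used to summarize PFS over time", followed by "The 6-month PFS with 95% confidence interval will be reported". It does not restate the test, a threshold or the interval method.

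**The concern.** One number appears in two roles: a floor in Section 11.2 and a promising target in Section 11.3.1. No written rule acts on it. The interim rule works at 15%, and the powered comparison is with 15.8%. The paragraph that should close the matter reports estimates only.

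Taken at face value, a final estimate of about 27% would beat history on the powered test and still fall short of the stated floor. A result of 3 out of 20 progression-free would be clearly below 35% on one interval method and not on another. In a 20-patient single-arm trial, pre-specification is the main guard against choosing the reading after the data are seen. An undefined criterion for dropping the regimen therefore deserves a check.

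**Working it through.** **Inputs.** From Section 11.3.1: reference 15.8%, benchmark 35%, hazard ratio 1.76, one-sided 0.05, n = 20, exponential PFS, 5 years of accrual plus 1 year, and a Beta(1,4) prior with stopping if Pr(PFS < 0.15) is at least 0.80 at 8 patients and every 4 thereafter. From Section 11.2: 35% as the floor.

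**1. What 35% does in the design.** Hazards are −ln(0.158)/6 = 0.3075 and −ln(0.35)/6 = 0.1750 per month. Their ratio is 1.758, the plan's 1.76. So 35% is the alternative on which the trial was sized.

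**2. The plan's power.** With 20 events and total follow-up T, 2 × 0.3075 × T is chi-square on 40 degrees of freedom under the null. The 95th percentile is 55.76. Power = Pr(chi-square(40) > 55.76/1.758) = 82.2% (82.3% with 1.76), against the stated 82%. The implied test is thus identifiable from the sample-size paragraph.

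**3. Where that test succeeds.** It rejects when the estimated hazard is at most 0.3075 × 40/55.76 = 0.2206. That is an estimated 6-month PFS of at least exp(−6 × 0.2206) = 26.6%. Any test with power above about 50% at its alternative has its cut-off on the null side of that alternative. Requiring an observed 7/20 or more (35%) would give only 58.3% power at a true 35%, at a one-sided level of 2.9%.

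**4. The interim rule.** The posterior Pr(PFS < 0.15) is as follows:

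| Progression-free | Posterior | Stop? |
|---|---|---|
| 0/8 | 0.858 | yes |
| 1/8 | 0.557 | no |
| 0/12 | 0.926 | yes |
| 1/12 | 0.716 | no |
| 1/16 | 0.824 | yes |
| 2/16 | 0.595 | no |

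With complete 6-month status, the stopping probability is q^8 + 8p·q^15, where q = 1 − p. This gives 34.8%, 12.7% and 3.6% at true 15.8%, 25% and 35%. The plan's own interim table shows 0.12 at 25% and 0.04 at 35%. Putting 35% into this rule would not work: the prior alone gives Pr(PFS < 0.35) = 1 − 0.65^4 = 0.82, already past the 0.80 trigger. The re-derivation put stopping at about 50% of trials with a true PFS of 35%.

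**5. Do the two readings the text supports collide?** They are (i) beats 15.8% on the implied test, and (ii) is clearly worse than 35%, read as an upper 95% limit below 35%. With 20 events the lower hazard limit is the estimate × 24.43/40 = 0.611 × estimate. The upper PFS limit is therefore (estimated PFS)^0.611. It falls below 35% when the estimate is below 0.35^(1/0.611) = 17.9%. Reading (i) needs 26.6%, so the regions are disjoint.

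A simulation of 200,000 trials per scenario used exponential PFS, entry every 3 months, analysis at month 72, the interim rule on complete 6-month status, and a likelihood-ratio form of the test. Reading (i) was met in 4%, 35% and 79% of trials at true 15.8%, 25% and 35%. Both readings together occurred in:

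| Interval for (ii) | Trials meeting both, true PFS 15.8% to 35% |
|---|---|
| Hazard-based | none |
| Exact binomial | under 0.02% |
| Kaplan-Meier log-log | 0.06% to 0.34% |

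**6. How far the interval method matters.** Upper 95% limits, exact and log-log: 2/20, 31.7% and 27.2%; 3/20, 37.9% and 33.5%; 4/20, 43.7% and 39.3%. Exact and log-log part company only at 3/20. After interim stopping, that outcome arises in about 18%, 10% and 2.5% of trials at true 15.8%, 25% and 35%.

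**The case for a change.** The strongest case for a change is that a power alternative is not a decision criterion. Section 11.2 gives 35% a decision role, and nothing carries it out. With 2/20 progression-free the posterior probability of being below 35% is 0.997, yet no rule fires, because the probability of being below 15% is only 0.72. The chance of a favourable conclusion at a true 25% also runs from 21% (observed 35% or more), through 35% (beats 15.8%), to 74–84% (not clearly worse than 35%). Only Stratum 2 is called exploratory, so Stratum 1 should have a settled criterion.

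Part of this stands. The qualifier in "PFS that is convincingly worse than this would be considered grounds for discontinuing further study" is undefined, the two descriptions of 35% differ, and the closing paragraph neither restates the test nor names the interval.

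The wide range carries less weight. Its lowest figure comes from a rule that fails any estimate below 35%, which appears nowhere in the plan. Section 11.2 counts only clear inferiority to 35% against the regimen. The other two figures answer different questions: whether the regimen beats history, and whether the benchmark has been ruled out. A trial can properly do neither, and the reported interval will show that. The 2/20 example would also mislead no one: its exact interval, 1.2% to 31.7%, lies wholly below 35%.

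**Conclusion.** The concern does not call for a change. The null, alternative, level, sidedness and power are all in Section 11.3.1 and agree with one another. The interim rule is deliberately lenient, and its properties are tabulated. An analyst following the text would report the Kaplan-Meier and hazard estimates with 95% intervals, set them beside 15.8% and 35%, and apply the one-sided test on which the trial was sized. That is a sound analysis for a study of this size.

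The silence on what clearly worse than 35% means, and on the interval method, is missing detail. Exact and log-log limits disagree at one outcome, 3/20, and the two criteria the text supports contradict each other in about 0.3% of trials at most. A graded decision scheme at 35% would be a matter of preference and would leave sample size, level and interim looks as they are.

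This rests on exponential PFS, on the final test being the hazard test implied by the sample-size paragraph, on complete 6-month status at interim looks, and on reading clear inferiority as an upper 95% limit below 35%.
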